- 5) Mean arterial blood pressure (MABP) < 35 mmHg despite therapy with volume infusions and vasoactive inotropes.
- **6)** Impaired kidney function; and prior administration of pulmonary vasodilators or prior administration of surfactant.

Methods of the study:

Patients included in the study were subjected to the following:

Complete history taking: Full antenatal and postnatal histories.

were obtained from all cases including:

- Demographic data (gestional age, sex, mode of delivery, birth weight).
- Associated condition (asphyxia, infection, polycythemia).

Clinical examination:

Full clinical examination: including general examination included vital signs, anthropmetric measurements, APGAR score in the 1st and 5th minutes (7).

systematic examination including chest and abdominal examination with emphasize on the cardiac examination including the apex site, 1st, and 2nd heart sounds and manifestations of heart failure (tachycardia, tachypnea and enlarged liver), musculoskeletal and central nervous system examination.

Radiological investigation

- Chest X-ray
- ECG: The ECG may provide suggestive or supportive evidence of pulmonary hypertension by demonstrating RV hypertrophy and strain, and right atrial dilatation
- ECHO: measures pulmonary artery pressure, low ventricular output and low ejection fraction and fraction shortening.

Laboratory analysis

- Pulse oximeter monitoring in the four limbs:
- Blood pressure monitoring in the four limbs.
- Serial arterial blood gases: Post ductal arterial blood samples were drawn before (baseline) and 6, 12, and 24 h following study drug administration for gas analysis PH, PaO2, PaCO2, HCO3).
- Ventilatory parameters were recorded from ventilator (PIP, PEEP, MAP, fiO2, rate/min).
- serum magnesium level was measured before and 12 h following study drug administration.

The protocol of administration of magnesium sulfate:

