- For intravenous administration a magnesium sulfate 10% solution was prepared by diluting an intravenous form of magnesium sulfate heptahydrate 50% with glucose 5%. Pharmacy designed 60mL aliquots of magnesium sulfate 10% and similar aliquots of glucose 5% as a placebo was prepared. Study participants received either active drug or placebo through an intravenous line a loading dose of 2 mL/kg over 30 min (equivalent to magnesium sulfate 200 mg/kg in case of the active drug), followed by a continuous infusion at a rate of 0.5 mL/kg/h (equivalent to magnesium sulfate 50 mg/kg/h in case of the active drug) for the 24 h study duration.
- For nebulization, an isotonic solution of magnesium sulfate (64 mg/mL) was prepared by diluting an intravenous form of magnesium sulfate heptahydrate 10% with distilled sterile water, 4-ml aliquots of isotonic magnesium sulfate (256 mg) and similar aliquots of isotonic saline as a placebo was designed. a 4-mL aliquot of active drug or placebo was loaded every 15 min to the jet nebulizer of ventilator.

The primary outcome in this study has been the change in oxygenation index (OI) from baseline to 12 and 24 h following study drug administration. OI: monitoring the oxygenation trend helps to guide when a baby might need to be referred for ECMO. It is a useful guide to monitor regularly in babies with PPHN.

OI: Mean Airway Pressure x FiO2 x 100 ÷PaO2 (in Pka) x 7.5

OI was preferred as it considers both oxygenation status and ventilatory support, over merely reporting individual values of SpO2, PaO2, FiO2, and ventilatory parameters. Note: When you are calculating OI, be aware of which units of measurement you use for the PaO2 – kPa or mmHg (kPa x 7.5 converts to the equivalent PaO2 in mmHg). FiO2 is the inspired fraction (e.g. 21% = 0.21, 100% = 1.0)

The secondary outcomes have been the changes in (a) mean arterial pressure and VIS from baseline to 6, 12, and 24 h following study drug administration and (b) serum magnesium level from baseline to 12 h after study drug administration.

Statistical analysis

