The data were coded, entered and processed on computer using SPSS (version 24). The results were represented in tabular and diagrammatic forms then interpreted. Mean, standard deviation, range, frequency, and percentage were use as descriptive statistics. The following tests were done: Chi-Square test X² was used to test the association variables for categorical data. Student's t-test was used to assess the statistical significance of the difference between two population means in a study involving independent samples, with normal distribution. The accepted level of significance was 0.05. P value >0.05 is non-significant, P<0.05 is significant (*)

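### Arterial pressure, VIS and serum magnesium are planned only as mean changes, so the trial as written gives no proportion of infants harmed by either route

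*Combined protocol and SAP*

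**What the plan says.** All references are to the combined protocol and SAP.

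- **Outcomes** (paragraph just before Statistical analysis): "The secondary outcomes have been the changes in (a) mean arterial pressure and VIS from baseline to 6, 12, and 24 h", and then "serum magnesium level from baseline to 12 h after study drug administration". Each is defined as a change. None has a threshold or a count.
- **Magnesium sampling** (Laboratory analysis): "serum magnesium level was measured before and 12 h following study drug administration". There is one sample after baseline.
- **Pressure figure** (Exclusion criteria, item 5): "Mean arterial blood pressure (MABP) < 35 mmHg despite therapy with volume infusions and vasoactive inotropes". This is the only pressure threshold in the document. It applies at entry and is qualified by failure to respond to therapy.
- **Comparison of means** (Statistical analysis): "Student's t-test was used to assess the statistical significance of the difference between two population means in a study involving independent samples".
- **Categorical data** (Statistical analysis): "Chi-Square test X² was used to test the association variables for categorical data". No categorical harm variable is named for this test.
- **Description** (Statistical analysis): "Mean, standard deviation, range, frequency, and percentage were use as descriptive statistics". The list is generic and tied to no outcome.

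The document names no adverse-event outcome and gives no magnesium limit.

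**The concern.** The trial compares two routes of a systemically active drug, so a reader will want to know how many infants on each route had low pressure or high magnesium. The planned analysis answers a different question, whether the average change differs between arms.

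Harm of this kind depends on the level that an individual infant reaches. For pressure, a marked fall in a few infants is diluted by the rest of the arm. For magnesium, a larger mean rise with the intravenous route is expected from the design, so its P value says little about safety. A change score also drops the starting level: an infant with a higher baseline can show a modest rise and still have the highest 12 h value.

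The Statistical analysis section labels P>0.05 as non-significant. Followed as written, the report could state no significant difference in arterial pressure while several infants in one arm had large falls, with no proportion affected for either route.

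**Working it through.** The plan has no figure of its own to reproduce here. It gives 20 infants per group and a 0.05 level, but no SD, effect size or event rate. Every SD and baseline below is an assumption.

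**1. Dilution of a few large falls.** Suppose *k* of 20 infants in one arm fall by a further 15 mmHg and no one else is affected. SD of change: 5 to 8 mmHg.

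- Shift in arm mean = 15*k*/20: 2.25 mmHg for *k* = 3, 3.0 mmHg for *k* = 4.
- Extra variance in that arm = 225 × *k*(20 − *k*)/(20 × 19). For *k* = 3 this is 225 × 51/380 = 30.2.
- *k* = 3, SD 5: pooled variance = (25 + 30.2 + 25)/2 = 40.1; standard error = √(40.1 × 2/20) = 2.00; typical t = 2.25/2.00 = 1.12.
- *k* = 3, SD 8: pooled variance = (64 + 30.2 + 64)/2 = 79.1; standard error = 2.81; typical t = 0.80.
- The two-sided 5% critical value on 38 degrees of freedom is 2.02, so both fall well short.

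Share of simulated trials with t-test P<0.05 (at least 20,000 per setting; ranges cover repeat runs):

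| Infants affected | SD 5 | SD 6 | SD 8 |
|---|---|---|---|
| 3 of 20 | 14% | 12% | 9-10% |
| 4 of 20 | 22-23% | 19% | 14% |

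**2. What a count would give.** Exact (Clopper-Pearson) 95% intervals:

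- 0/20: upper limit 1 − 0.025^(1/20) = 16.8%.
- 3/20: 3.2% to 37.9%.
- 4/20: 5.7% to 43.7%.

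Fisher's exact test, two-sided, against 0/20: 3/20 gives 2 × C(20,3)/C(40,3) = 2 × 1140/9880 = 0.23; 4/20 gives 0.11; 5/20 gives 0.047. With fewer than 10 events in total, the expected event cells (total/2) are below 5, so the listed chi-square test would not suit.

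Chance of seeing at least one case in 20: 1 − 0.95^20 = 64% at a true rate of 5%, and 1 − 0.90^20 = 88% at 10%.

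**3. Does a count below 35 mmHg recover the affected infants?** Only partly. Assume baseline means of 42-55 mmHg (SD 5-7, all at least 35 at entry), SD of change 5-8, three infants with the extra 15 mmHg fall, and one on-treatment reading.

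- Of the three, on average 0.7 to 2.6 are below 35.
- In an arm with no affected infant, on average about 0.04 to 3.9 of 20 are below 35.
- The affected arm shows exactly 3/20 in only 2-32% of trials.

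The count therefore depends heavily on baseline pressure and must be shown with it.

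**The case against.** **The range is listed, so extremes would be visible.** Partly right. The descriptive list is not confined to change scores, so an extreme level might be reported, and it would be too strong to say that affected infants can never appear. But the range is not tied to these outcomes or to levels, and no range says how many infants were affected.

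**35 mmHg is not a safety limit.** Correct. A reader might infer that the plan sets a safety limit on treatment and then fails to monitor it. The document does not support that: the figure is an entry exclusion, qualified by response to therapy. It serves only as a ready reference value for description.

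**Other safety-related data are collected.** Also correct. VIS sits in the same outcome as arterial pressure, and vital signs, pulse oximetry, serial blood gases and four-limb blood pressure are recorded. It would be wrong to say that magnesium and pressure are the only such data. VIS matters most here. Reading it as a vasoactive-inotropic score (the document does not expand it), an infant whose pressure was held up by more inotropic support would show the problem there and not in a pressure count.

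**A count can also mislead.** Step 3 of the working bears this out. A reader might infer that counting shows the affected infants directly; it does not.

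**The magnesium argument is weaker in this population.** Recent maternal magnesium and impaired kidney function are excluded, which removes two obvious causes of a high baseline. One 12 h sample can miss a peak after the 30-minute load or late in the infusion, and a count above a laboratory limit may largely restate the route.

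**It is late to prespecify.** The study ran to September 2023, the document is dated 2025, and the analysis section is in the past tense. A threshold chosen now may be post hoc and must be labelled so.

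None of this supplies the missing harm proportion. It limits what the remedy can claim.

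**Conclusion.** The point holds in this form: arterial pressure, VIS and magnesium are planned as changes compared on means, and no per-infant count or adverse-event outcome is specified, so neither route gets a harm proportion.

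The size of the dilution rests on assumed SDs of 5-8 mmHg and a fall of 15 mmHg confined to a few infants. Under those assumptions the planned test would miss the difference in roughly 86-90% of trials with 3 of 20 affected, and 77-86% with 4 of 20. The absence of a planned count does not depend on these figures.

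The documents do not show that any infant was harmed, and the primary outcome is unaffected. This is a worthwhile, cheap improvement in reporting. It cannot turn 20 infants per arm into a test of safety.

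**What to change.** Add one descriptive safety table by arm, as n/20 with exact 95% intervals:

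- **Pressure with VIS.** Infants with any 6, 12 or 24 h mean arterial pressure below 35 mmHg, described as the plan's entry-exclusion figure and not as an on-treatment safety limit. Show each such infant's baseline pressure and change in VIS. List change in VIS for the other infants too, so that pressure held up by added support is visible.
- **Magnesium.** The 12 h level itself beside the change, the maximum per arm, a plot of individual values, and the number above an external limit that the investigators state and justify. Label the limit post hoc if analysis has begun.

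Keep the mean changes. State that P>0.05 on them is not evidence of safety. If the counts are tested at all, use Fisher's exact test.

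State the limits with the table: wide intervals, low power for any test on the counts, a pressure count that depends on baseline, and a single post-baseline magnesium sample that can miss peaks.

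The cost is a short SAP addition, one small table and one plot from existing data. This changes reporting only; no dose, treatment rule or toxic level is proposed.
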